#### PROTOCOL TITLE: Lifestyle Intervention in Preparation for Pregnancy (LIPP) VERSION DATE: March 31st, 2023

consisting of dietary guidance, free fitness club membership, and personal coaching initiated between 10-14 weeks' gestation (18) reported that although there was a decrease in GWG in the intervention group (7.0 vs. 8.6 kg, p=0.01), paradoxically infants in the lifestyle intervention group had higher birth weight (3,742 vs. 3,593 g, p=0.04) compared to controls. Other recent RCTs (UPBEAT and the Norwegian Fit for Delivery Trial) suggest that behavioral lifestyle interventions do not prevent GDM or reduce the incidence of LGA babies despite reducing maternal dietary glycemic load, GWG, and maternal skinfold measures, and increasing physical activity (22,23). At least five meta-analyses published in the past four years, all concluded that lifestyle interventions initiated during pregnancy, while having some success in reducing excessive GWG, had minimal positive effects on adverse pregnancy outcomes including decreasing fetal overgrowth (24, 25, 26, 27, 28). Although some advocate weight loss in obese women during pregnancy, these recommendations are based on extrapolation of epidemiological data (29, 30, 31). Investigators in the UPBEAT trial noted that increasing the intensity and duration of the lifestyle intervention was likely to be impractical for most obese women (22) Further, we reported an increased risk of small for gestational age (SGA) neonates and decreased lean body mass (head circumference and length) in neonates of overweight/obese women with inadequate GWG (32).

**Post-delivery weight loss: is it possible and safe, and what is the effect on subsequent pregnancies?** Publications related to postpartum weight loss have been primarily retrospective cohort studies reporting that ~10-20% of overweight/obese women had a decrease in weight between pregnancies (33, 34, 35, 36). The interval between pregnancies was 12 months in 30% and 24-36 months in 40-57% of subjects (34, 37). Inter-pregnancy weight loss in overweight/obese women was associated with a decreased risk of GDM or preeclampsia (35, 36, 38, 39) in a subsequent pregnancy. Three studies reported a decreased incidence of LGA in overweight/obese women who had an inter-pregnancy decrease of as little as 1-2 BMI units (34, 37, 38). The inter-pregnancy decrease in weight was not associated with an increased risk of SGA infants (34).

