In order to ensure safety with the nutrition intervention, all food provided to subjects as part of this study will be prepared by the HNRCA or BWH Research Facility research nutrition team in the metabolic kitchen of the HNRCA or Research Facility or if the visits are taking place at the CTRC, food provided will be prepared by the nutrition team in the Tufts Medical Center kitchen. The diet will be based upon the Mediterranean diet, which is an eating pattern that focuses on fruits, vegetables, legumes, nuts, lean proteins and fish, while limiting red meats and sweets high in added sugar. Additionally, olive oil is used as the main fat in the diet. The caloric needs of the participants in the lifestyle modification program will be calculated from resting metabolic rate, which will be measured by indirect calorimetry, adjusted initially by a factor of 1.3 to account for the exercise program. Further adjustment in caloric content will be made to attain a weight loss of >5% of pre-pregnancy weight or closest weight to pre-pregnancy based on best clinical data. This will be achieved by a negative caloric balance of 500 Kcal/day to attain a rate of weight loss of 1 lb/week. Participants will be instructed by the LIPP team so dietary intake includes healthy choices for fat (mono and polyunsaturated) and protein (fish, nuts, legumes, and poultry) and substitution of dietary fat and simple sugars by healthy carbohydrates (fruits, vegetables, whole grains). If weight loss is not being achieved, participants will be recommended to use meal replacements (commercially available) to facilitate caloric restriction as was used with great success in the Look AHEAD trial. Once the weight loss target is attained, subjects will enter into a maintenance dietary phase, the aim of which will be to maintain or reduce further weight (up to 15% of baseline weight).

During pregnancy, subjects randomized to the lifestyle intervention program will be advised to maintain their exercise regimen as tolerated per ACSM and ACOG guidelines. During pregnancy, all subjects will have dietary recommendations based upon the ACOG guidelines and delivered by the clinical nutrition program at Tufts Medical Center and Brigham & Women's Hospital in order to gain weight as recommended by the 2009 IOM guidelines. Drs. [name] and [name] will oversee the studies in the HNRCA and [name] and [name] will oversee the studies in the BWH Research Facility.

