Our over-arching hypothesis is that the maternal pre-pregnancy metabolic condition determines the obesogenic in-utero environment, which affects programming of placental mitochondrial function and metabolic pathways, promoting lipid accumulation and neonatal adiposity. Our rationale is based on the need to establish the most effective time to introduce an intervention that will break the obesity cycle in mothers and their children. Understanding how pregravid metabolic conditioning improves maternal physiology and cellular and molecular function in pregnancy will provide the empirical data to support the intervention. We have a highly successful record of - recruiting women who are planning a pregnancy, obtaining compliance in longitudinal studies, and in long-term follow-up of mothers and their offspring. Lifestyle intervention will be initiated prior to conception to decrease maternal body fat, inflammation, insulin resistance, and  $\beta$ -cell dysfunction. Our trans- disciplinary team has the required expertise in lifestyle interventions, management of obesity, and in human physiology that is needed to determine the effects of these interventions on maternal metabolism and fetal- placental growth and function. We will recruit 200 women to pursue the following specific aims:

Specific Aim 1: To investigate the physiological significance of lifestyle intervention in preparation for pregnancy (LIPP) on maternal and neonatal metabolism and adiposity.

Sub-Aim 1a. The working hypothesis is that a lifestyle intervention, initiated after the index pregnancy, will facilitate lower maternal insulin resistance, inflammation, weight, adiposity, incretin response, and energy expenditure compared to usual care. We will perform longitudinal measures of body composition, insulin sensitivity and secretion and blood markers of inflammation. We will link these changes to improvements in neonatal adiposity and insulin sensitivity.

Sub-Aim 1b. The working hypothesis is that women who initiate a lifestyle intervention before the subsequent pregnancy will deliver a baby with lower birth weight and fat accretion; insulin resistance; and cord blood markers of inflammation. We will measure body composition using anthropometrics and air displacement plethysmography (Pea Pod), umbilical cord glucose, insulin, leptin, IL-6, hsCRP, and adiponectin.

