#### 8.2 Statistical Analysis

• Describe the statistical analyses that will be performed for this study **Statistical Analysis** 

The primary analyses of Specific Aim 1a will be intent-to-treat comparisons of the LIPP and Control groups in regard to changes in maternal insulin sensitivity, BMI, and fat mass. The comparisons will be performed first with two-sample t-tests at  $\alpha$ =0.05. Should any imbalance of confounding factors in the groups be recognized, linear regression models that include significant differences (e.g. GDM) would be used to perform covariate adjustments. Based on our 1-year postpartum follow-up studies (62,63), we will have 90% power to detect an absolute or covariate-adjusted improvement in insulin sensitivity of 30% and an 80% power to detect an improvement as small as 25% in the LIPP vs. Control group. Corresponding 95% confidence intervals (95% CI) for the absolute or covariate-adjusted differences or percent improvements in insulin sensitivity between groups will be reported. We estimate the standard deviation (SD) of change in BMI from randomization until subsequent pregnancy to be 5.1 kg/m2. We will have 90% power to detect an absolute or covariate-adjusted difference in BMI of 2.6 kg/m2 and 80% power to detect a difference of 2.26 kg/m2 and 90% power to detect an absolute or covariate-adjusted difference in fat mass of 5.9 kg and 80% power to detect a difference of 5.1 kg between groups prior to the second pregnancy. The primary analysis for Specific Aim 1b is an intent-to-treat comparison of LIPP versus Control neonates with respect to fat mass at birth. The comparison will be performed using a two-sample t-test at  $\alpha$ =0.05. Linear regression will be performed, which will include weight (body composition measures) of the subject's index child as a covariate. Should any imbalance of confounding factors (for example gestational age) in the groups be recognized, linear regression models will be used to perform a covariate adjustment. Based on our preliminary data, we estimate the SD of neonatal fat mass between the LIPP and Control groups to be no more than 225 g. With at least 50 women in each group, (assuming a 50%) dropout), the t-test or linear regression will have 90% power to detect an absolute or

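### The SD of BMI change behind the Aim 1a power (5.1 kg/m2) has no source and looks too large, and the stated detectable differences need about 80 women per group, not 50

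*Combined protocol and SAP*

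**What the plan says.** Section 8.2 (Statistical Analysis) makes changes in maternal insulin sensitivity, BMI and fat mass the primary analyses of Aim 1a. On the test it says: "The comparisons will be performed first with two-sample t-tests at" the 0.05 level. For BMI it gives one planning input, "We estimate the standard deviation (SD) of change in BMI from randomization until subsequent pregnancy to be 5.1 kg/m2", and claims "90% power to detect an absolute or covariate-adjusted difference in BMI of 2.6 kg/m2 and 80% power to detect a difference of 2.26 kg/m2". For fat mass it gives detectable differences of 5.9 kg (90% power) and 5.1 kg (80%) but no SD. Neither the BMI nor the fat-mass claim states a sample size.

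Later in the same section, for the neonatal outcome of Aim 1b, the sample size is given: "With at least 50 women in each group, (assuming a 50%) dropout". This matches section 3: "We will recruit 200 women to pursue the following specific aims".

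Two other places bear on the BMI figures. The nutrition text in section 2.2 (Protection Against Risk) aims to "attain a weight loss of >5% of pre-pregnancy weight" and then to "maintain or reduce further weight (up to 15% of baseline weight". The background in section 2.1 cites reports of fewer large-for-gestational-age infants in "overweight/obese women who had an inter-pregnancy decrease of as little as 1-2 BMI units".

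**The concern.** The insulin-sensitivity and cord-blood figures in section 8.2 refer to earlier studies. The 5.1 kg/m2 does not, and the BMI claims rest on it. It is labelled an SD of within-woman change, which is normally smaller than the spread between women because a woman's earlier and later BMI are correlated. Here it exceeds the widest spread that the 25-35 entry range allows.

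At stake is whether the Aim 1a power statement describes the planned comparison. If 5.1 is right, the trial has little power for a difference equal to the programme's own minimum goal. If it is too large, the stated detectable differences are wrong in the other direction. In both cases the sample size behind the BMI claim is missing and does not match the one the section uses elsewhere.

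**Working it through.** **Inputs.** SD of change 5.1; differences 2.6 (90% power) and 2.26 (80%); alpha 0.05; 50 per group after dropout (all section 8.2). Entry BMI 25-35 (section 4.1). Goals of more than 5% and up to 15% (section 2.2). Assumed: two-sided test and 1:1 allocation, neither of which is stated.

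**Step 1: reproduce the plan's figures.** Detectable difference = SD × (z for alpha + z for power) × √(2/n), where the z sum is 3.2415 for 90% power and 2.8016 for 80%.
- n = 50: 5.1 × 3.2415 × 0.2 = 3.31 and 5.1 × 2.8016 × 0.2 = 2.86 (t-test: 3.34 and 2.89).
- n = 80: 5.1 × 3.2415 × 0.1581 = 2.61 and 5.1 × 2.8016 × 0.1581 = 2.26 (t-test: 2.63 and 2.27).

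Solving for n gives 81 and 80 per group (t-test: 82 and 81). The stated pair therefore fits about 80 per group, a number the documents never give. At 50 per group the power for 2.6 and 2.26 is 72% and 60%. At 60 per group (40% dropout) it is 80% and 68%; at 100 per group, 95% and 88%. To obtain the stated differences with 50 per group, the SD would have to be 2.6 / (3.2415 × 0.2) = 4.0. By contrast, the neonatal fat and birth-weight figures reproduce at 50 to 51 per group.

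**Step 2: set 5.1 against the entry range.** Over 25-35, a uniform distribution has SD 10/√12 = 2.89. The maximum, with half the women at each limit, is 5.0. (Mixing in the Asian range widens the span to 23-35. Its theoretical maximum of 6.0 would need half the women at 23 and half at 35; uniform gives 12/√12 = 3.5.) With equal SDs s before and after, the SD of change is s√(2(1 − ρ)), so ρ = 1 − 5.1²/(2s²). At s = 2.89, ρ = 1 − 26.01/16.67 = −0.56. With an assumed ρ of 0.8 the SD of change would be 2.89 × √0.4 = 1.8. To reach 5.1 at that ρ, the follow-up SD would have to be about 7.1. An SD of 5.1 also spreads 95% of changes over ±1.96 × 5.1 = ±10 kg/m2 around the mean, if roughly normal.

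**Step 3: implied fat-mass SD.** From 5.9 kg at 90% power: 5.9 / (3.2415 × 0.2) = 9.1 kg at 50 per group and 5.9 / (3.2415 × 0.1581) = 11.5 kg at 80 (t-test: 9.0 and 11.4). The 5.1 kg figure at 80% power gives the same values.

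**Step 4: compare with the goals.** Five percent of BMI 25-35 is 1.25-1.75 kg/m2; fifteen percent is 3.75-5.25. The stated differences run from 2.26/35 = 6.5% to 2.6/25 = 10.4% of BMI.

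**Step 5: sensitivity** (t-test; SDs of 2.0-3.0 are assumptions; 1.5 kg/m2 is 5% of BMI 30).

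| SD of change | Detectable 90% / 80%, n = 50 | Detectable 90% / 80%, n = 80 | Power for 1.5, n = 50 | Power for 1.5, n = 80 |
|---|---|---|---|---|
| 2.0 | 1.31 / 1.13 | 1.03 / 0.89 | 96% | 99.7% |
| 2.5 | 1.64 / 1.41 | 1.29 / 1.11 | 84% | 97% |
| 3.0 | 1.96 / 1.70 | 1.55 / 1.34 | 70% | 88% |
| 5.1 | 3.34 / 2.89 | 2.63 / 2.27 | 31% | 46% |

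**The case against.** The entry criterion limits pregravid BMI at the index pregnancy. It does not limit BMI at three months postpartum, later BMI, or change. The 15% ceiling is a goal for individuals in the intervention arm and not a bound on spread; controls may gain. This stands: a reader might infer that 5.1 contradicts the protocol, but the documents show only that it is implausible.

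A reader might also infer that the detectable differences exceed the loss the programme targets. They do not. The goal starts above 5% and runs to 15%, and 6.5-10.4% lies inside it. Only the 5% minimum is exceeded. That minimum also refers to pre-pregnancy weight, whereas the analysed change starts at randomization. The tested quantity is the difference between arms, and section 2.1 reports that 84% of an earlier cohort of 126 women gained weight between pregnancies, so control-arm gain could widen the contrast. The plan states no expected difference. The 1-2 BMI units in the background come from retrospective cohorts and are not used as a design effect.

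Finally, the value is close to the cross-sectional BMI SD of 5.2 in the team's earlier trial of 24 obese adults (section 2.1), which invites the reading that a between-woman SD was used by mistake. That is inference: section 8.2 labels 5.1 an SD of change, and the underlying data are not shown.

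The objection does not account for the missing source or the sample-size mismatch.

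**Conclusion.** The concern holds in a limited form. The 5.1 kg/m2 is unsourced and implausibly large as an SD of change in this population, and the fat-mass claim rests on a similarly large SD that is not stated. With SD 5.1 the BMI differences hold at about 80 per group; at 50 per group they are 2.9 (80% power) and 3.3 (90% power).

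A reader might conclude that Aim 1a is badly underpowered. That follows only if 5.1 is right and the true contrast is near the 5% minimum. If 5.1 is too large, the error is conservative: at an assumed SD of 2.5, power for 1.5 kg/m2 with 50 per group is 84% instead of 31%. The effect is on the stated power for Aim 1a. The t-test and regression will use the observed variance, and the primary outcome, neonatal adiposity (section 8.1), has its own SD and sample size. The sample-size result assumes a two-sided test with equal allocation. The plausibility argument also depends on assumed BMI distributions and correlation.

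**What to change.** In section 8.2:
- Give the source of 5.1 kg/m2 and confirm whether it is an SD of change or a between-woman SD.
- Replace it with the SD of baseline-adjusted change in BMI from visits already completed, pooled across arms without arm labels. Do the same for fat mass and state that SD. A label-free SD absorbs part of any arm difference, but little: with SD 2.5 and a difference of 1.5, √(2.5² + 1.5²/4) = 2.61.
- State the n per group used for each Aim 1a claim, and whether the test is two-sided.
- Restate the detectable differences, and add the power at the 5% minimum.

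The cost is one masked tabulation and revised wording. Section 8.3 says women have already been recruited in Cleveland and Baton Rouge, and section 8.5 keeps the analysing statistician blinded. No analysis method, visit or recruitment target has to change.

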# 4.3 Withdrawal of Subjects

Subjects who do not become pregnant at the end of the intervention or usual care component (21 months postpartum) are still included in the study. They will not undergo further evaluation but will continue to be followed until either they become pregnant or the study terminates. Contact will be maintained through a brief monthly check-in phone call from study staff. For the intervention arm, this will include a reminder of body weight goal and strategies to sustain weight loss. Testing will resume during pregnancy at the specified intervals of 12-16 and 32 to 36 weeks of pregnancy.

• Describe anticipated circumstances under which subjects will be withdrawn from the research without their consent.

We have had subjects we asked to withdraw from the study because of their not returning for their metabolic assessments in the metabolic research centers, no shows at scheduled training sessions, smoking (which is an exclusion criteria).

If a LIPP subject becomes pregnant prior to 16 weeks after randomization or becomes pregnant before the 3-month postpartum randomization, i.e. no baseline measurement, they would be asked to withdraw.

• Describe procedures that will be followed when subjects withdraw or are withdrawn from the research, including the possibility of partial withdrawal from study intervention with continued data collection.

We will plan to maintain demographic data for subjects who have withdrawn from the study in order to compare with subjects who have been compliant with the study protocol in order to determine if there was bias in subject compliance.

• Include any necessary safety precautions to be applied to subjects who withdraw or are withdrawn (tapering drug doses, evaluative x-ray, etc.). NA

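### Aim 1a compares maternal changes over a window that ends at conception, with no rule for its unequal length or for women who do not conceive

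*Combined protocol and SAP*

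**What the plan says.** Section 8.2 labels the primary analyses of Specific Aim 1a as intent-to-treat "comparisons of the LIPP and Control groups in regard to changes in maternal insulin sensitivity, BMI, and fat mass". On method it says: "The comparisons will be performed first with two-sample t-tests". Adjustment is conditional on what is seen in the data: "Should any imbalance of confounding factors in the groups be recognized, linear regression models that include significant differences" would then be used. Follow-up time is not named as a covariate.

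No analysis visit is named. The timing has to be read from the power statement, which puts an SD of 5.1 kg/m2 on the "change in BMI from randomization until subsequent pregnancy", from the fat-mass power sentence, which refers to the time before the second pregnancy, and from Section 8.1, which places the maternal outcomes before a subsequent pregnancy. The three agree.

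Section 5.1 calls the pre-pregnancy period variable. The minimum is about 4 months in study, and evaluations at 3, 6, 9, 15 and 21 months postpartum continue until pregnancy, up to 18 months in study. Section 4.4.3 gives five postpartum visits as a maximum.

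Section 4.3 addresses "Subjects who do not become pregnant at the end of the intervention or usual care component", at 21 months postpartum. These women remain in the study but have no further evaluation unless they conceive. Women who conceive within 16 weeks of randomisation are asked to withdraw.

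**The concern.** A change score compared by t-test estimates a clear quantity when every woman is measured over the same interval. Here the interval is set by conception. Two women in the same arm may contribute changes over 4 and 18 months, and the test treats them alike.

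Conception follows randomisation, and weight loss or better metabolic function may alter when it happens. If the arms differ in time to conception, part of the estimated effect is a difference in elapsed time. The estimate also averages over different amounts of intervention.

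For women who do not conceive, the window has no end point. They can have measurements up to 21 months postpartum, but no rule says which of these, if any, enters the comparison. That choice could be made after the data are seen.

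The intermediate visits have no role as repeated measures. Baseline enters only by subtraction, and the two randomisation strata in Section 8.5 are not planned covariates.

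**Working it through.** **1. The plan's own figure.** Inputs from Section 8.2: SD of BMI change 5.1 kg/m2, alpha 0.05, and detectable differences of 2.6 kg/m2 (90% power) and 2.26 kg/m2 (80% power). Two-sided testing and 1:1 allocation are assumed; neither is stated.

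n per arm = 2 × (SD/difference)² × (z for alpha + z for power)²

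- 2.6 at 90%: 2 × (5.1/2.6)² × (1.960 + 1.282)² gives 81.
- 2.26 at 80%: 2 × (5.1/2.26)² × (1.960 + 0.842)² gives 80.

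At 80 per arm the noncentral t gives power 0.893 and 0.795, so the figures reproduce. A one-sided test would need 66 and 63, which do not agree on one group size.

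**2. What 80 per arm implies.** With 200 women (Section 3), it means 80 of every 100 contribute, a 20% loss. With the total of 220 in Section 8.3, it means 80/110 = 73%. Neither share is stated. For Aim 1b the same section assumes 50% loss and 50 per arm, and Section 8.3 expects 40 to 50% dropout in Greater Boston. Noncentral t, SD 5.1:

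| n per arm | Power for 2.6 | Power for 2.26 | Detectable at 80% power (kg/m2) |
|---|---|---|---|
| 100 | 0.948 | 0.877 | 2.03 |
| 80 | 0.893 | 0.795 | 2.27 |
| 60 | 0.791 | 0.673 | 2.63 |
| 50 | 0.714 | 0.593 | 2.89 |

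**3. Effect of unequal timing.** The documents give no BMI trend and no conception times by arm, so this is an illustration. Suppose both arms follow the same BMI trend and the intervention has no effect on it, but the mean window differs between arms. Then bias = trend × timing gap. The standard error at 80 per arm is 5.1 × √(2/80) = 0.806.

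| Trend (kg/m2 per month) × gap (months) | Bias (kg/m2) | Two-sided type I error |
|---|---|---|
| 0.05 × 2 | 0.1 | 0.052 |
| 0.05 × 4, or 0.1 × 2 | 0.2 | 0.057 |
| 0.1 × 4, or 0.2 × 2 | 0.4 | 0.079 |
| 0.2 × 4 | 0.8 | 0.168 |

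With no gap, the error stays at 0.05.

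**4. Baseline as a covariate.** With equal variances at baseline and follow-up and correlation r, the change score has variance 2(1 − r)σ² and the baseline-adjusted outcome (1 − r²)σ². The ratio is (1 − r²)/(2(1 − r)) = (1 + r)/2, which cannot exceed 1. It is 0.75 at r = 0.5 and 0.90 at r = 0.8, but the documents give no r, so no specific gain is claimed. The formula also fits the stated SD poorly at high r. A change SD of 5.1 with r = 0.8 implies a BMI SD of 5.1/√0.4 = 8.1, while Section 4.1 limits pregravid BMI for most women to 25 to 35, a range whose largest possible SD is 5. BMI at 3 months postpartum may spread more widely, but 8.1 is hard to credit.

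**The case against.** The strongest reply is that the phrase about conception sits in a variance assumption and does not define an analysis set, that the analysis is labelled intent-to-treat, and that the scientific question really is the mother's condition before the next pregnancy. On that view, a fixed visit answers a different question. It would miss status just before conception in women who conceive late, and would be missing because of conception in women who conceive early. Much of this stands. A fixed-visit contrast is a trade-off, and a mixed model must still handle visits lost to conception. But an intent-to-treat label does not supply an endpoint time, and no other text does.

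Several stronger readings are tempting but not supported:

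- A reader might infer that women who do not conceive are excluded. No text says so, and Section 4.3 keeps them in the study. What is missing is a rule for the value they contribute.
- A reader might infer that the maternal effect is estimated in about half the women. The 50 per arm belongs to the neonatal and cord-blood outcomes; the BMI figures imply about 80. The 45% conception rate by 24 months in Section 2.1 comes from a database not restricted to women planning pregnancy, and that section expects shorter intervals in this trial.
- A reader might put the gain at 30%, from 2.89 to 2.03 kg/m2. That compares 50 with 100 per arm. From the implied 80, the change is 2.27 to 2.03, about 11%, and 100 per arm requires no loss at all.
- A reader might assume that all women have five postpartum visits. Five is the maximum, and the series stops at conception.
- A reader might say baseline is ignored. A change score uses it, though not as a covariate.

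Finally, Section 8.1 lists the maternal outcomes as secondary. The neonatal primary outcome is unaffected.

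**Conclusion.** The point holds as a defect of definition and analysis in Aim 1a. The comparison uses a window of about 4 to 18 months that ends at a post-randomisation event, takes no account of its length, and is undefined for women who do not conceive.

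The size of any bias cannot be known from the documents. Under the assumed trends and timing gaps it is 0.1 to 0.8 kg/m2, with type I error of 0.052 to 0.168; it needs a difference between arms in timing, which is possible but not shown.

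The BMI power is internally reproducible at about 80 per arm, assuming 1:1 allocation and two-sided tests, but that number is not stated or justified. Losses for maternal outcomes may legitimately be lower than for neonatal ones, since a woman who does not conceive can still give maternal data. If only 50 per arm contribute, power is 0.71 and 0.59.

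This should be corrected before the data are analysed. It does not threaten the trial's primary outcome.

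**What to change.** Rewrite the Aim 1a analysis in Section 8.2 as follows.

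- Analyse each maternal outcome in all randomised women with a linear mixed model over all available pre-pregnancy visits. Include arm, visit, arm-by-visit interaction, baseline value, the two stratification factors (overweight vs obese, breastfeeding status) and site.
- Name one visit for the main contrast. An earlier visit loses fewer women to conception; a later one reflects more of the intervention. Keep the last pre-conception change as a supporting analysis.
- State how women who do not conceive, and women asked to withdraw after early conception, contribute. Treat visits missing because of conception as missing at random given observed values, with a sensitivity analysis that relaxes this.
- State the number per arm and allocation ratio behind the BMI power. Either justify about 80 per arm or restate the detectable differences; at 50 per arm the figure at 80% power is 2.89 kg/m2.

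The cost is plan wording and a standard model, with no new data or visits. The downsides are that a fixed-visit contrast is not the same as status immediately before conception, and that later visits lean on the missing-data assumption. The supporting and sensitivity analyses address these in part. The mixed model itself cannot be sized from the documents, which give no within-woman correlations.

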## 8.3 Number of Subjects

- If this is a multicenter study, specify the number of subjects to be enrolled in total across all sites. 220.
- Specify the number of subjects to be enrolled at the Tufts site. Subjects who sign an ICF are considered "enrolled". For studies that have a separate screening ICF, this number is the number of subjects who sign a screening ICF. 100
  - Provide the rationale for enrolling this number of subjects at the Tufts site.
     This is approximately 50% of the study recruitment goals of 200. In addition to the already recruited participants in Cleveland and Baton Rouge, the Boston sites anticipate to recruit the remaining subjects to meet the goals.
  - Estimate the number of subjects expected to be enrolled at the Tufts site (i.e. sign the screening or study ICF) as well as the number needed to complete the study at the Tufts site.
     We anticipate recruiting 100 subjects in the Greater Boston area and expect a 40 to 50% dropout for various reasons.
  - If a large number of withdrawals and/or dropouts are expected, explain why.
     It is not unusual for a lifestyle intervention study lasting over a number of years to have a 40% dropout rate. This has been addressed in the statistical analysis.

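### The Aim 1a BMI power figures need about 80 women per group, a number the plan never states and its own 40–50% dropout does not leave

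*Combined protocol and SAP*

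**What the plan says.** Section 8.2 lists BMI among the primary intent-to-treat comparisons of Aim 1a, tested first with two-sample t-tests at alpha 0.05. The variability input is: "We estimate the standard deviation (SD) of change in BMI from randomization until subsequent pregnancy to be 5.1 kg/m2". The power claim is: "We will have 90% power to detect an absolute or covariate-adjusted difference in BMI of 2.6 kg/m2 and 80% power to detect"; the figure given for 80% is 2.26 kg/m2. No sample size or loss rate accompanies these figures.

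The first sample size in the section comes later, in the Aim 1b neonatal fat-mass calculation: "With at least 50 women in each group, (assuming a 50%) dropout". Birth weight and cord cytokines also use 50 per group, and Aim 2 uses 18 per group.

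Section 8.3 gives two totals. One is a form prompt with its answer: "specify the number of subjects to be enrolled in total across all sites. 220". The other appears in the rationale for the 100 subjects at the Tufts site: "This is approximately 50% of the study recruitment goals of 200". On loss, the Greater Boston recruiters "expect a 40 to 50% dropout for various reasons", and a multi-year lifestyle study is said not unusually to "have a 40% dropout rate. This has been addressed in the statistical analysis".

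Section 4.3 adds: "Subjects who do not become pregnant at the end of the intervention or usual care component (21 months postpartum) are still included", although they have no further evaluation unless they conceive.

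**The concern.** A power statement can be checked only when its n is known. Here the n has to be inferred, and the inferred value does not match any recruitment and dropout combination in the plan. Section 8.3 tells the reader that heavy dropout is already allowed for in the statistical analysis, but no such allowance is visible in the BMI figures.

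What is at stake is how an Aim 1a BMI result is read. A null finding would be set against a claim of 90% power for 2.6 kg/m2, when power under the plan's own dropout could be nearer 71–79%.

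**Working it through.** **Inputs.** SD 5.1 kg/m2, differences 2.6 and 2.26 kg/m2, powers 90% and 80%, alpha 0.05 (all section 8.2). Two assumptions are needed. The test is taken as two-sided, because sidedness is not stated. Allocation is taken as 1:1, because no ratio is stated, but 50 per group after 50% loss from 200 implies it.

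**Formula.** Detectable difference = (z_0.975 + z_power) × SD × √(2/n), with n per group. The sum of the z values is 3.2415 for 90% power and 2.8016 for 80%.

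**Check on figures whose n is stated.** Neonatal fat mass, SD 225 g, n = 50, √(2/50) = 0.2:
- 90%: 3.2415 × 225 × 0.2 = 145.9 g (plan: 146)
- 80%: 2.8016 × 225 × 0.2 = 126.1 g (plan: 126)

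Birth weight, SD 700 g, comes out at 453.8 and 392.2 g (plan: 455 and 393), which is close. A one-sided test would give 131.7 and 111.9 g for fat mass, so the plan's calculation is two-sided.

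**The n implied by the BMI figures.** n = 2 × [(z_0.975 + z_power) × SD / difference]²:
- 2.6 at 90%: 2 × (3.2415 × 5.1 / 2.6)² = 80.9
- 2.26 at 80%: 2 × (2.8016 × 5.1 / 2.26)² = 79.9

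The t-test calculation gives 81.8 and 80.9. In the other direction, n = 80 in the normal formula gives 2.61 and 2.26 kg/m2. Because the plan rounds, only about 80 is supported, not an exact integer; both powers are met within two percentage points for n from 77 to 85.

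**Implied loss.** 2 × 80 = 160 evaluable women. 1 − 160/200 = 20%; 1 − 160/220 = 27%.

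**Group sizes the plan states or implies, against 80** (t-test, SD 5.1):

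| n per group | Origin | Power for 2.6 | Power for 2.26 | Detectable at 90% / 80% (kg/m2) |
|---|---|---|---|---|
| 50 | 200, 50% loss | 71% | 59% | 3.3 / 2.9 |
| 55 | 220, 50% loss | 75% | 63% | 3.2 / 2.7 |
| 60 | 200, 40% loss | 79% | 67% | 3.0 / 2.6 |
| 66 | 220, 40% loss | 83% | 71% | 2.9 / 2.5 |
| 80 | not stated | 89% | 80% | 2.6 / 2.3 |
| 100 | 200, no loss | 95% | 88% | 2.3 / 2.0 |
| 110 | 220, no loss | 96% | 91% | 2.2 / 1.9 |

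Only the unstated 80 returns the plan's pair of figures.

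**Covariate adjustment.** For 2.6 kg/m2 to have 90% power at 50 per group, the residual SD would have to be 3.97, so covariates would have to explain 1 − (3.97/5.1)² = 39% of the variance (about 27% at 60 per group). The plan gives no such value and claims the same figures for the unadjusted difference.

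**The case against.** The strongest reply is that nothing is miscalculated. The SD and both differences agree with each other at about 80 per group, and the shortfall appears only if dropout quoted for other purposes is carried over to BMI. The 50% belongs to Aim 1b, which needs a delivered and measured infant. The 40–50% concerns completing the study in Greater Boston, which runs through delivery. Weight, by contrast, is measured at visits up to 21 months postpartum (section 5.1), and women who have not conceived remain in the study. Section 2.1 reports that only 32% of the investigators' database conceived within 18 months and 45% within 24, although shorter intervals are expected here. Lower loss for BMI than for neonatal outcomes is therefore credible.

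Much of this stands: the 71–79% is conditional, not demonstrated. But the plan never makes the argument, and section 8.3 offers no loss rate below 40%. The argument also meets a difficulty in the plan's own definition. The SD is for change up to the next pregnancy, a time point that women who never conceive do not have. Retaining them helps the BMI comparison only if the endpoint is set at a visit they attend.

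It is also fair that BMI is not the trial's main question. Section 8.1 makes maternal weight and body composition secondary outcomes, even though section 8.2 calls BMI a primary analysis of Aim 1a.

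**Conclusion.** The concern holds. The stated 90% and 80% power for BMI require about 80 evaluable women per group, and no combination of the plan's totals (200 or 220) with its dropout (40–50%) leaves that many. If that dropout applies, power is 71–79% for 2.6 kg/m2 and 59–67% for 2.26 kg/m2 from 200 recruited, or 75–83% and 63–71% from 220. If loss for BMI really is about 20% from 200 (27% from 220), the figures are right but unsupported by anything written.

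This rests on a two-sided 0.05 test, 1:1 allocation and the plan's SD of 5.1. It should be corrected, but its reach is limited: the primary neonatal fat-mass power reproduces at 50 per group and is not affected.

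**What to change.** In section 8.2, state the number per group and the assumed loss for the Aim 1a BMI comparison, and say which total (200 or 220) it starts from. Then do one of two things:

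- **(a) Use the plan's own dropout.** With SD 5.1, from 200 recruited, restate the detectable differences as about 3.3 kg/m2 (90%) and 2.9 kg/m2 (80%) at 50 per group, or about 3.0 and 2.6 at 60 per group.
- **(b) Keep the present figures.** State that about 80 per group is intended, justify the loss of roughly 20% from 200 (27% from 220), and define the BMI endpoint at a pre-pregnancy visit that women who have not conceived also attend.

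The same n statement could usefully cover insulin sensitivity and maternal fat mass. Their power figures also lack an n and, having no SD, cannot be checked at all.

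The cost is wording in section 8.2, with no change to recruitment or the primary outcome. Option (a) makes the stated detectable differences less favourable; option (b) also commits the trial to a fixed BMI time point.
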